Protocol Title: Effect of Ultrasound Guided Laser Ablation Therapy on Symptomatic Benign Thyroid Nodules

Funding agency: Elesta S.p.A.

National Clinical Trials Number (NCT): NCT04277455

Principal Investigator: [name]
Mercy Clinic Endocrinology
[name]
[name]
[name]
[contact]

Sub-Investigator: [name]
Mercy Clinic Endocrinology
[name]
[name]
[contact]
[contact]

Study Site: Mercy Clinic Endocrinology
[name]
[name]

Study Methods

The primary objective of this study was to assess the effectiveness of percutaneous laser ablation under ultrasound guidance for the treatment of symptomatic benign thyroid nodules. The secondary objectives were to examine the safety and tolerability of this treatment technique.

The study was approved by the Mercy institutional review board and Investigational Device Exemption was obtained from the US Food and Drug Administration.

Device

The ECHOIASER X4 laser system (ElestaSpA) and its disposable kit (needle and optical fibers) have been Conformite Europeenne- marked for marketing in Europe since 2008. In addition, the ECHOIASER X4 laser system received US Food and Drug Administration 510(k) Premarket Notification approval as a substantially equivalent device on September 4, 2018. The ECHOIASER X4 system is a medical laser equipped with up to 4 diode laser sources at 1064-nm wavelength, with a maximum power of 7 W per source.

Study Population

The inclusion criteria consisted of the following: male or female aged ≥ 18 years, thyroid-stimulating hormone (TSH) levels within normal limits, solid thyroid nodule with $<20\%$ cystic component measuring

between 29 mm and 60 mm in the longest dimension as confirmed by ultrasound imaging, symptoms from the nodule, such as tightness or pressure in the neck, neck tenderness, neck pain, difficulty swallowing, voice changes, shortness of breath, or cosmetic disfigurement, nodule confirmed as cytologically benign by biopsy within 2 years, ability to place the laser tip inside the nodule while keeping vital structures outside the zone of injury, with a minimum distance of 17 mm anterior to the vital structures and 10 mm in all other dimensions based on the planning software, not on anticoagulants or the ability to stop anticoagulants for an appropriate period based on the pharmacology of the drug, and able and willing to provide informed consent.

The exclusion criteria for the study were as follows: pregnancy, hyperthyroidism, malignant thyroid nodule, egg-shell or coarse calcification in the thyroid nodule on ultrasound imaging, being on anticoagulation that cannot be stopped because of medical reasons, coagulopathy, a thyroid nodule in contact with the trachea, esophagus, or major blood vessels on ultrasound imaging, prior neck surgery, prior radiation to the head and neck, previous radioactive iodine treatment, current iodine supplementation, current antithyroid medication, biotin supplementation within 2 days before enrollment, allergy or contraindication to use of ChloraPrep and/or Betadine products and/or product ingredients, allergy to ethyl chloride spray or lidocaine, physical or psychological conditions preventing safe administration of the procedure, and individuals who cannot read and understand English. Written informed consent was obtained from all patients.

Study Design and Intervention

This was a single-center, prospective, nonrandomized, open-label, interventional pilot study.

Baseline assessments included history and physical examinations, visual inspection of the neck at 1 m, symptom, and cosmetic disfigurement survey (TSH, Free 14, Free 13, and antithyroid anti-bodies were obtained if not completed within 3 months before enrollment) and an ultrasound of neck with Doppler. A biopsy with fine needle aspiration was performed if a biopsy had not been performed within 2 years of enrollment and/or if a benign nodule had grown >30% in the last 2 years or there was development of new suspicious sonographic features.

All enrolled subjects underwent pre-procedure direct laryngoscopy performed by otolaryngology to assess vocal fold mobility and establish the baseline status of vocal fold structure and function.

At the study treatment visit, history and physical examinations, visual inspection of thyroid/neck at 1 m, symptom and cosmetic disfigurement surveys, qualitative β -human chorionic gonadotropin for women of childbearing potential, prothrombin time/ international normalised ratio for patients on anticoagulants, and ultrasound of thyroid/neck with Doppler were performed.

Anticoagulation medications were stopped 48 hours before the laser ablation procedure and antiplatelet medications were stopped 72 hours before the laser ablation procedures for subjects taking these medications. Subjects were permitted to take a one-time dose of a prescribed oral anxiolytic; alprazolam 0.5 mg, lorazepam 0.5 mg, or clonazepam 0.5 mg for acute procedural anxiety one hour before the procedure if indicated by the study investigator ([name]) after discussion with the subject.

Laser precautions were followed. The procedure was performed using a sterile technique under sterile conditions.

The planning of the laser ablation procedure, insertion of needles, and monitoring of the procedure were carried out with ultrasound guidance. The Echolaser Smart Interface (ESI, Elesta SpA) facilitated the insertion of the needles and the positioning of the needles into the target lesion. The laser energy

was transmitted from the laser energy source via bare-tip optical fibers (flat-tipped quartz optical fibers with a diameter of 300 µm, Oberon GmbH). The fiber was inserted into the thyroid nodule using a 21-gauge needle introducer. Guidance was provided by the ESI and verified using ultrasound. The ESI guiding systems have been designed to help the operator position several fibers inside the lesion to be treated. The software displays the guidelines on the screen for each different guide and angle for evaluation of the best positioning of the applicator in reference to the size, morphology, and position of the lesion. After the introducer needles have been positioned, the ESI allows for verification of the needle position using the effective needle position recalculating the estimated thermal treatment area. ESI estimates the zone of injury to avoid damage to vital structures.

The fiber and needle are the only system components that come into contact with the patient and they come prepackaged as sterile disposable (single-use) kits. The optical fiber and needle are provided in ethylene oxide sterilized packaging. The total energy to be applied was calculated based on the manufacturer's guidelines. After completion of laser ablation, the fibers were removed followed by extraction of the needle(s), and hemostasis was achieved by application of pressure at the site. External bleeding was assessed by visual inspection following extraction of the needle. Internal bleeding and potential nodule rupture were assessed by ultrasound of the neck with Doppler flow performed by the investigator.

Baseline vital signs were obtained before the start of the procedure. Subjects were monitored closely during the procedure and continuous heart rate and oxygen saturation monitoring was performed. Subjects were observed in the clinic for a minimum of one hour after the procedure with procedure site inspection and examination of vital signs performed.

Subjects were asked to complete a pain assessment before the procedure and a pain assessment and tolerability assessment before discharge from the clinic. Subjects were contacted by telephone within 2 days after the study procedure for follow-up and assessment of adverse events.

Follow-up visits were performed at 3, 6, and 12 months after completion of the study procedure. History and physical examinations, visual inspection of thyroid/neck at 1 m, and ultrasound of thyroid/neck with Doppler were performed at all visits. A pain assessment was performed at 3 months and the symptom and cosmetic disfigurement surveys were performed at all visits. TSH and Free T 4 were obtained at 3 and 6 months and TSH, Free T 4, and antithyroid antibodies were collected at the 12th month of follow-up visit. Adverse events were monitored throughout the study. Physical examinations, visual inspection of neck region at 1 m, ultrasound with Doppler examinations, and the laser ablation procedure were performed by the same investigator for all subjects.

Data Collection and Statistical Analysis

Visual inspection of the neck region was performed at a distance of 1 m from the subject. The presence or absence of a cervical lesion was documented using the following scale: 1 - nodule not visible; 2 - nodule visible only with hyperextended neck; and 3 – nodule visible at a distance > 1 m. All ultrasound examinations of the neck with Doppler were performed using the GE Logiq P6 ultrasound. The nodule volume (in ml) was calculated using the following equation: volume = length (cm) x width (cm) x depth (cm) x 0.52ⁱ. The nodule volume percent was calculated using the following equation: volume reduction percentage = (1 - final volume/initial volume) x 100.ⁱⁱ Results of laboratory assessments obtained as described above were collected. For pain assessment, subjects were asked to rate their neck pain on a scale from 0 to 10, where 0 indicated no pain and 10 indicated worst pain possible. Subjects that reported neck pain were asked to indicate the location of the pain. Local symptoms were evaluated with a questionnaire adapted from the questionnaire used in the study

conducted by Papini et al.ⁱⁱⁱ The questionnaire assesses the presence or the absence of the following symptoms: neck constriction, cervical tenderness, dysphagia, dyspnea, and dysphonia. In addition, subjects were asked whether the thyroid nodule is causing cosmetic disfigurement to assess the cosmetic impact of their thyroid nodule on a scale from 0 to 10 where 0 indicated not at all and 10 indicated very much. Tolerability assessment was performed after the procedure using a questionnaire consisting of the following 3 questions with Likert scale responses: How likely is it that you would have the laser ablation procedure again? How satisfied were you with the length of the laser ablation procedure? How much discomfort did you have with the laser ablation procedure? The pain, symptoms, and cosmetic and tolerability assessments were performed for subjects.

ⁱ Seo SH, Kim TH, Kim SH, et al. Predicting the size of benign thyroid nodules and analysis of associated factors that affect nodule size. *Chonnam Med J*. 2015;51(2):97-101.

ⁱⁱ American Thyroid Association. Change in thyroid nodule volume calculator. Accessed June 21, 2023.

<https://www.thyroid.org/professionals/calculators/thyroid-with-nodules/>

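### Does the neck-visibility scale leave a nodule ungraded because inspection is at 1 m but grade 3 refers to more than 1 m?

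*Combined protocol and SAP*

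**What the plan says.** The combined protocol and SAP names one inspection distance throughout. Under Study Design and Intervention:

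- Baseline includes "visual inspection of the neck at 1 m".
- The treatment visit includes "visual inspection of thyroid/neck at 1 m, symptom and cosmetic disfigurement surveys".
- For the visits at 3, 6 and 12 months the text has "visual inspection of thyroid/neck at 1 m, and ultrasound of thyroid/neck with Doppler were performed at all visits".

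Data Collection and Statistical Analysis then introduces the scale with "Visual inspection of the neck region was performed at a distance of 1 m from the subject". Its three grades are:

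- 1: "nodule not visible"
- 2: "nodule visible only with hyperextended neck"
- 3: "nodule visible at a distance > 1 m"

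Grade 3 gives no neck position, and no inspection from beyond 1 m is described. The rater is the same person throughout: "visual inspection of neck region at 1 m, ultrasound with Doppler examinations, and the laser ablation procedure were performed by the same investigator". This holds for every subject. The section defines the volume calculation and the volume reduction percentage. It sets out no analysis of change in visibility grade.

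**The concern.** A three-step scale should give each finding one grade, and the examiner should be able to observe what each grade describes. Taken word for word, this scale does neither. A nodule visible at 1 m with the neck neutral, but from no farther, is not grade 1 (it is seen), not grade 2 (it needs no hyperextension) and not grade 3 (it is not seen beyond 1 m). From 1 m the examiner cannot directly separate that finding from a true grade 3.

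The setting adds to the worry. The study is open-label, and the investigator who performs the ablation also rates the neck at every visit. Cosmetic disfigurement is one of the qualifying symptoms, so a before-and-after comparison of visibility is a natural use of these data. If the unwritten rule drifted from the higher to the lower grade between baseline and follow-up, some apparent improvement would come from coding alone.

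**Working it through.** The plan states no figure for this outcome, so there is none to reproduce. The check is to list the possible findings and map each to a grade as worded.

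| Finding | Literal grade |
|---|---|
| (a) Not visible in either neck position | 1 |
| (b) Visible only on hyperextension, at 1 m but not beyond | 2 |
| (c) Visible in neutral position at 1 m but not beyond | none |
| (d) Visible in neutral position at 1 m and beyond | 3 |
| (e) Visible beyond 1 m, only on hyperextension | 2 and 3 |

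So there is one gap, (c), and one overlap, (e).

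**How wide is the gap?** Grade 3 requires visibility at more than 1 m and names no further distance. A nodule still visible slightly beyond 1 m qualifies. State (c) therefore needs visibility to end almost exactly at 1 m. Visibility fades gradually with distance, so few nodules should fall there. For the same reason, an examiner who plainly sees a nodule at a nominal 1 m can reasonably infer that it would be seen from slightly farther.

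**Does the scale resolve the overlap?** The same continuity means that most nodules seen at 1 m only on hyperextension would also be seen on hyperextension from slightly farther. If grade 3 ignored neck position, it would absorb nearly all of grade 2. The middle grade has a purpose only if grade 3 refers to the neutral neck. On that reading, (e) is grade 2 and anything seen in neutral position is grade 3, including (c).

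**What could miscoding do?** Let g be the share of subjects in state (c) at both visits, and p0 and p1 the chances that it is coded 3 at baseline and at follow-up. Treating the two ratings as independent:

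- false improvement = g × p0 × (1 − p1)
- false worsening = g × (1 − p0) × p1
- net = g × (p0 − p1)

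Under the sensible reading p0 = p1 = 1, and all three are zero whatever g is. A net effect needs both a sizeable g and a shift in convention. As an assumed illustration, a shift from 0.8 to 0.6 gives a net 0.05 × 0.2 = 1% at g = 5%, 0.10 × 0.2 = 2% at g = 10%, and 0.20 × 0.2 = 4% at g = 20%. The documents support none of these inputs, and the knife-edge argument puts g well below that range. Any coding of (c) as 2 would also contradict the word 'only' in grade 2.

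The formula covers only subjects in state (c) at both visits. For a subject who moves from (c) to hyperextension-only, coding (c) as 3 counts an improvement and coding it as 2 counts none. The natural reading again settles this, and such subjects are few if (c) is nearly empty.

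**What depends on the grade?** Volume reduction comes from ultrasound dimensions. The cosmetic score is reported by the subject. Grade 1 against grades 2 and 3 combined depends only on whether the nodule is seen. None of these changes with the treatment of (c) or (e).

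**The case for a change.** The strongest contrary case is that a written rule matters most with a single unmasked rater, and the plan has none. A reader of the results cannot tell from the document which convention was applied, one sentence would settle it, and the scale is recorded at five time points (baseline, treatment, 3, 6 and 12 months) in a study whose primary objective is effectiveness. Calling the symbol a slip for 'at least' is a guess, since the document does not say so.

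Part of this stands. The wording is imprecise and no coding rule is given. I do not rely on a misprint either: an at-least sign appears correctly in the age criterion, so an error in the symbol is possible but not shown. The step from imprecise wording to a material risk does not stand. The grade definitions already exclude grades 1 and 2 for a nodule seen in neutral position, so the rater had no real choice between 2 and 3. A single rater is a reason for caution about masking, but it also favours a stable convention. The harm described would arise in a grade-change analysis that the document does not contain.

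**Conclusion.** The literal gap and overlap exist, but they need no change to the plan. The mismatch is a clerical imprecision that a sensible reader resolves in one way: visible in neutral position at the 1 m inspection is grade 3, and visible only on hyperextension is grade 2. On that reading the scale is exhaustive, its grades do not overlap, and all can be observed from 1 m.

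The expected effect on grade changes is zero among subjects in the ungraded state at both visits, and negligible otherwise. No number in the documents supports a larger estimate. The conclusion rests on three assumptions: visibility declines gradually with distance, the one investigator coded consistently across visits, and visibility grade stays a descriptive measure without an endpoint role. The document is written in the past tense, so new wording would not recode ratings already made, and it would alter neither volume reduction nor the cosmetic score.

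### Does the plan need to say which pre-ablation visit supplies the initial volume, and to use the duplicate pre-treatment measurements?

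*Combined protocol and SAP*

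**What the plan says.** Under Study Design and Intervention, the protocol describes the trial thus: "This was a single-center, prospective, nonrandomized, open-label, interventional pilot study".

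The same section sets out the pre-ablation measurements at two points:

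- At baseline: "Baseline assessments included history and physical examinations", followed by "visual inspection of the neck at 1 m, symptom, and cosmetic disfigurement survey" "and an ultrasound of neck with Doppler".
- On the day of treatment: "At the study treatment visit, history and physical examinations, visual inspection of thyroid/neck at 1 m, symptom and cosmetic disfigurement surveys", with a pregnancy test and coagulation tests "for patients on anticoagulants, and ultrasound of thyroid/neck with Doppler were performed".

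Follow-up visits are at 3, 6 and 12 months. Each repeats the ultrasound, the inspection and both surveys.

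Data Collection and Statistical Analysis computes volume from three ultrasound dimensions and then defines change as "volume reduction percentage = (1 - final volume/initial volume) x 100". It gives no rule for which visit is initial or final, no summary statistic, and no use for the second set of pre-treatment values.

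Study Population admits nodules "between 29 mm and 60 mm in the longest dimension as confirmed by ultrasound imaging" and requires at least one complaint due to the nodule. The documents give neither the number of patients nor the time between the baseline and treatment visits.

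**The concern.** With two candidate starting values and three candidate end values, the reported reduction depends on an unstated choice, and an unstated choice can be made after the results are known.

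The design adds to the worry. There is no control arm, subjects are not blinded, and one investigator does the scans, the inspections and the ablation. Patients enter because a nodule measured long enough and because they had a symptom. Both conditions can produce apparent improvement without treatment, through regression to the mean and measurement error. The pre-treatment pairs are the only scheduled within-patient evidence on that, and the plan does not say it will look at them. If untreated drift were large, part of the benefit credited to ablation would not be due to it.

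**Working it through.** The documents state no sample size, measurement error, symptom prevalence or expected reduction, so there is no figure of the plan's to reproduce. **Every numerical input below is an assumption, apart from the 29 to 60 mm entry limits and the formula.**

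**1. How far the choice of initial scan moves the result.** Let r be treatment-visit volume divided by baseline volume, and take a patient with a 50% reduction from baseline. Measured from the treatment visit, the reduction is 1 - 0.5/r.

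| r | Reduction from treatment visit |
|---|---|
| 0.8 | 37.5% |
| 0.9 | 44.4% |
| 1.1 | 54.5% |
| 1.2 | 58.3% |

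These are single-patient shifts. What matters for the group is the average drift, taken next.

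**2. Expected drift in volume with no true change.** Nodules were simulated (2,000,000 per setting) with log-normal true length (log SD 0.25) and selected on a measured length of 29 to 60 mm. Log-volume error SD was s, shared across the three axes. The qualifying scan was taken as initial. Apparent reduction in geometric mean volume:

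| Median true length | s = 0.10 | s = 0.15 | s = 0.20 |
|---|---|---|---|
| 30 mm | 0.89% | 2.04% | 3.56% |
| 34 mm | 0.55% | 1.20% | 2.10% |
| 38 mm | 0.23% | 0.53% | 0.91% |
| 45 mm | -0.19% | -0.44% | -0.75% |

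The spread of true length also matters. At 30 mm and s = 0.20, a log SD of 0.15 gives 5.3% and one of 0.35 gives 2.5%. A fair range is therefore about 5% shrinkage to 1% growth. At these extremes, a 50% group reduction from baseline becomes 1 - 0.5/0.947 = 47.2% or 1 - 0.5/1.0075 = 50.4% from the treatment visit, a shift of less than 3 points.

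**3. Expected drift in symptoms with no true change.** A simple formula for the net fall in one item's prevalence is (1 - kappa) × (p/P(any) - p). Here p is prevalence before selection, kappa is retest agreement (0.6 to 0.9), and P(any) is the chance of at least one of 5 to 7 items, with latent correlation 0 to 0.6.

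- p = 80%: 0 to 1.2 points.
- p = 50%: 0.04 to 5.1 points. With five independent items and kappa 0.6 it is 0.4 × (0.5/0.969 - 0.5), about 0.6 points.
- p = 20%: 0.5 to 9.8 points.

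The upper ends come from high correlation between items, yet the formula gives the other items no role in predicting the retest. If that correlation is a stable trait of the patient, simulation puts the maxima at about 2 points (p = 50%) and 4.4 points (p = 20%).

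**4. What the pairs could show.** The 95% half-width for mean log-volume change is t(0.975, n-1) × √2 × s/√n.

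- n = 30, s = 0.10: 2.045 × 1.414 × 0.10/√30 = 0.053, or -5.1% to +5.4%. The drift at s = 0.10 in the table is below 1%.
- n = 10, s = 0.20: 2.262 × 1.414 × 0.20/√10 = 0.202, or -18.3% to +22.4%. The drift at s = 0.20 is at most 3.6%, or 5.3% with the narrower length distribution.

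For the half-width merely to equal the drift, n must be about (1.96 × √2 × s/drift)², with drift on the log scale. That gives (0.2772/0.00894)², about 960 pairs, for 0.89% at s = 0.10. It gives (0.5544/0.0545)², about 104, for 5.3% at s = 0.20.

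For one symptom item the half-width is 1.96 × √(d/n), with d = 2(1 - kappa)p(1 - p). This gives 6.4 points at n = 30, kappa 0.9, p = 80%, and 27.7 points at n = 10, kappa 0.6, p = 50%. At n = 30, kappa 0.6 and p = 20% it is 1.96 × √(0.128/30) = 12.8 points, against a drift of 4.4 (stable trait) to 9.8 (simple formula).

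**The case for a change.** The strongest case for a change is that both steps cost almost nothing. Naming the visits takes a sentence and removes any choice after the fact. Tabulating the pre-treatment pairs uses data already scheduled, and in a single-arm, unblinded study even a rough bound on untreated change is better than none. Symptoms make the best case, because having one is an entry condition and the outcome is the subject's own report. The summary scale can matter too: with independent errors and no true change, the arithmetic mean of the ratio formula is 1 - exp(s²), an apparent growth of 1.0% to 4.1% at s = 0.10 to 0.20, even when the treatment-visit scan is initial.

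The visits are indeed unnamed, and a paired table would do no harm. The rest of the case is limited in four ways.

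- The plan names no arithmetic mean or any other summary, so the scale argument is directed at an analysis it does not state.
- The regression-to-the-mean calculation needs the baseline study scan and questionnaire to be what qualified the patient. The documents do not say so; earlier imaging or history may have done that.
- The comparison would be hard to read. The interval between visits is unstated, the same investigator makes both readings, and the treatment-day surveys may follow a permitted anxiolytic. A short interval shows repeatability, not a 12-month course.
- That the treatment-day measurements precede ablation, and that dimensions were recorded then, are reasonable inferences and not statements. The text is also in the past tense, so a rule fixed before analysis may no longer be possible.

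**Conclusion.** This is missing detail that analysts fill sensibly. One visit carries the baseline label, which makes it the natural initial value, and with scans at 3, 6 and 12 months the natural report is a reduction at each time. At the drift expected on the assumed inputs, taking the other pre-treatment scan would move a 50% group reduction by less than 3 points.

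The paired check could bound a gross drift. With 10 to 30 patients it could not resolve the expected one, which is about 5% shrinkage to 1% growth in volume and about 0 to 4 points per symptom item (up to about 10 under the simpler formula). It would not stand in for a control arm, so it is unlikely to alter a conclusion of this pilot.

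This rests on assumed error SDs of 0.10 to 0.20, retest agreement of 0.6 to 0.9 and 10 to 30 pairs. Visibility grade and cosmetic score were not quantified: visibility is not an entry condition and no cosmetic cut-off is given.

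### The five local symptoms are recorded only as present or absent, so the survey cannot show partial relief or worsening of a symptom that persists

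*Combined protocol and SAP*

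**What the plan says.** Under Study Methods, the primary objective is to "assess the effectiveness of percutaneous laser ablation under ultrasound guidance for the treatment of symptomatic benign thyroid nodules". Study Population makes symptoms from the nodule, or cosmetic disfigurement, a condition of entry.

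Data Collection and Statistical Analysis then describes the measures:

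- Local symptoms: "The questionnaire assesses the presence or the absence of the following symptoms", and the five listed are constriction, tenderness, dysphagia, dyspnea and dysphonia. The instrument is not taken over unchanged: "Local symptoms were evaluated with a questionnaire adapted from the questionnaire used in the study", the source being an earlier randomized trial of laser ablation. The adaptation is not described.
- Neck pain: "subjects were asked to rate their neck pain on a scale from 0 to 10".
- Cosmetic disfigurement: subjects are asked "to assess the cosmetic impact of their thyroid nodule on a scale from 0 to 10".
- Visibility, rated by the investigator: "1 - nodule not visible; 2 - nodule visible only with hyperextended neck; and 3 – nodule visible at a distance > 1 m".
- Nodule volume, as a percentage reduction.

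On follow-up timing, Study Design and Intervention says: "A pain assessment was performed at 3 months and the symptom and cosmetic disfigurement surveys were performed at all visits". Follow-up visits are at 3, 6 and 12 months. The symptom survey is also given at baseline and at the treatment visit. No sample size, significance level, test, primary endpoint or expected symptom response is stated.

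**The concern.** Effectiveness in symptomatic nodules is partly a question about symptoms. A yes/no item changes only when a symptom disappears or newly appears. The plan's anatomical outcome is a percentage reduction in volume, which allows for a nodule that is smaller but still there. A symptom that is milder but still there is then a plausible result, although no passage predicts it. For the five local symptoms the survey cannot tell that result from no change, nor from a persisting symptom that has become worse.

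At stake is the reading of the symptom results. A proportion with dysphagia that is the same at 12 months as at baseline could mean no benefit, or it could mean broad but incomplete relief.

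**Working it through.** The plan states no power or sample size, so there is no figure to reproduce. Steps 1 and 2 use the documents alone. Steps 3 to 6 use assumed values and are an illustration.

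**1. What an item can register.** Code an item 1 if present and 0 if absent. Its change is −1, 0 or +1. If severity goes from 8 to 2, or from 3 to 9, the item is 1 both times and the change is 0.

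**2. Which complaints are graded, and when in follow-up.**

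| Complaint | Format | Follow-up |
|---|---|---|
| Constriction, tenderness, dysphagia, dyspnea, dysphonia | present/absent | 3, 6, 12 months |
| Neck pain | 0–10 | 3 months only |
| Cosmetic impact | 0–10 | 3, 6, 12 months |

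At 6 and 12 months, cosmetic impact is the only graded self-report. Neither 0–10 scale covers constriction, dysphagia, dyspnea or dysphonia.

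**3. Resolutions needed for a detectable change.** Assume an exact two-sided McNemar test at 0.05. If all d changes go the same way, p = 2 × 0.5^d. For d = 5, p = 0.0625; for d = 6, p = 0.031. At least six subjects must lose the symptom.

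**4. Power of one yes/no item.** Take n = 20 subjects who all have the symptom at baseline, each resolving with probability q. Power = P(Binomial(20, q) ≥ 6).

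- q = 0.07: 0.2%
- q = 0.11: 1.8%
- q = 0.25: 38%
- q = 0.50: 98%

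**5. The same subjects on a 0–10 rating.** Assumed: baseline severity mean 6, SD 2, limited to 1–10; mean relative reduction 30%, 40% or 50%, with SD 40, 40 and 30 percentage points; follow-up rounded and limited to 0–10; paired t test. In simulation 7% to 11% of subjects reach zero, while 43% to 65% improve by at least 30% without reaching zero.

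| n with the symptom | Graded power | Yes/no power, absent only at 0 |
|---|---|---|
| 10 | 57% / 80% / 99% | 0% / 0% / 0% |
| 20 | 92% / 99% / 100% | 0.2% / 1.8% / 0.8% |
| 30 | 99% / 100% / 100% | 1.3% / 9.8% / 5.9% |

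**6. How far the yes/no figures depend on the assumptions (n = 20).**

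- If subjects answer absent at severity 1 or below, yes/no power is about 8% to 35%. At 2 or below it is 42% to 90%.
- With absent only at 0, mean reductions of 70% and 90% (SD 30 points) give about 39% and 98%.
- In a different model, 20 subjects are enrolled and 60% of them (about 20 × 0.6 = 12) have the symptom. Baseline severity has mean 5 and SD 2, and 5% of the others develop the symptom. Yes/no against graded power is then under 1% against 76% for a 30% fall, under 1% against 97% for 50%, 6% against 99% for 70%, and 46% against over 99% for 90%.

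In each of these settings the graded rating has at least the power of the yes/no item. The gap is very wide when symptoms mostly ease without clearing, and small when most symptoms clear.

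**The case against.** A reader might go further and infer that the pilot has almost no sensitivity to symptom benefit. The documents do not support that. Neck pain and cosmetic disfigurement are themselves qualifying complaints and are graded 0–10. Complete resolution of any of the five symptoms is still recorded. The near-zero power figures come from modest mean reductions combined with a rule that absent means exactly zero; step 6 shows what happens when either is relaxed.

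A reader might also infer that a subject who improves counts as unchanged. That is true of an item, not of a subject: someone who loses two of four symptoms registers as improved on two items.

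A third inference is that worsening goes unseen and safety is compromised. History and physical examination take place at every follow-up visit, there is a telephone contact within 2 days of the procedure, and adverse events are monitored throughout. Worsening can be picked up there, even though the survey will not show it.

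Two further arguments have weight. Keeping the yes/no format of a questionnaire from an earlier randomized trial is defensible in a pilot. And the plan names no test, so any power comparison is imposed from outside. In an open-label study without a control group, a fall in self-rated severity can also reflect expectation or regression to the mean, so high power for change is not high power for treatment benefit. Expectation affects a yes/no answer too.

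What remains is that partial change in five of the qualifying complaints is not measured, and that the two graded scales do not fill the gap. Adding a rating costs no comparability, because the yes/no answer stays and the questionnaire is already adapted.

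**Conclusion.** The point holds as a limited loss of information. Partial relief or worsening of a persisting local symptom is not captured by the survey, and this follows directly from the item format.

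The size cannot be fixed from the documents, which give no sample size, resolution rate or severity at which subjects answer absent. With 20 subjects who have the symptom, and the assumptions in steps 4 to 6, power for one yes/no item runs from under 1% to about 98%, against 92% or more for a graded rating. If only about 12 of 20 enrolled subjects have the symptom, graded power starts lower, at 76% for a 30% fall. These figures show the direction and range of the loss; they do not predict this trial's result.

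The change is worth making because it bears on effectiveness in symptomatic nodules and costs little.

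**What to change.** Keep the present/absent answer for each of the five symptoms and add a 0–10 severity rating in the anchor format already used for pain. Collect it at baseline, the treatment visit and 3, 6 and 12 months. Report within-subject change in severity among subjects who have that symptom at baseline, with the yes/no proportions alongside.

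The cost is five short ratings on a survey already given at each of these visits, with no extra procedure or staff. The ratings would have no counterpart in the source questionnaire and, like the yes/no items, would be open-label self-report.

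The text is in the past tense and cites a web page accessed in June 2023, so data collection may be complete. In that case, state the limitation, report the five symptoms as resolution or new onset only, and do not interpret an unchanged proportion as absence of benefit. This costs only a few sentences.
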